3 INTRODUCTION

CA2097G8 is a randomized, double-blind, Phase 3 trial of nivolumab or nivolumab-placebo in combination with intravesical bacillus Calumette-Guerin (BCG) in participants with recurrent or persistent high-risk non-muscle-invasive bladder cancer (NMIBC) after treatment with BCG who are not BCG unresponsive. Nivolumab is an immuno-oncologic checkpoint inhibitor that enhances T-cell anti-tumor activity. BCG treatment results in tumor inflammation, with the potential result of improved response to the combination of BCG and nivolumab.

The study aims to demonstrate that treatment with nivolumab in combination with intravesical BCG will improve event-free survival (EFS) vs intravesical BCG alone. Additional clinical endpoints include worsening-free survival (WFS), complete response rate (CRR) in participants with carcinoma in situ (CIS), and overall survival (OS). Additional objectives of the study include characterization of safety and tolerability, pharmacokinetics (PK), potential predictive biomarkers, and changes in patient-reported outcomes (PROs) for quality of life (QoL) assessment.

3.1 Study Rationale

Individually targeting immune checkpoint receptors such as programmed cell death protein-1 (PD-1) has demonstrated clinical activity across multiple tumor types, including advanced urothelial carcinoma (UC), for which several studies to date have demonstrated activity of therapeutic compounds aimed at the PD-1 receptor and its ligand, programmed cell death-ligand 1 (PD-L1).^{1,2,3}

In high-risk NMIBC, the standard of care (SOC) is transurethral resection of the tumor followed by intravesical BCG treatment. As BCG results in tumor inflammation and nivolumab enhances T-cell activity within the tumor, combining BCG with nivolumab may result in the potential for improved response of the tumor to immunotherapy.

3.1.1 Changes per Protocol Amendment 01

As of May-2021, the CA2097G8 study was behind its enrollment target. Bristol-Myers Squibb (BMS) undertook several mitigation actions to improve participant recruitment. Unfortunately, despite all efforts, the study was less than 5% of target enrollment since first patient first visit. Based on current timelines, the study would be unable to meet its scientific objectives in this evolving therapeutic landscape. As a result, a decision was made to close the study. It is important to note that there is no change to the understanding of the safety profile of nivolumab in combination with BCG for the participants with bladder cancer.

As of 02-Jun-2021 (Dear Investigator Letter; Approved v1.0 930170267), the following measures were put into effect:

- Enrollment for new participants was closed effective immediately.
- Participants who signed study consent prior to this notification and were undergoing screening were permitted to be randomized to study treatment.
- Participants on treatment were allowed to continue study treatment.

- For participants currently on efficacy follow-up, it is at the discretion of the investigator and participant whether to continue the efficacy follow-up, until Protocol Amendment 01 is approved by the relevant Health Authorities and Ethics Committees/Institutional Review Boards (EC/IRBs) at the site.

Protocol Amendment 01 describes the modification to study procedures. All participants must be re-consented upon approval and implementation of Protocol Amendment 01. These changes affect all participants and should be implemented when this Protocol Amendment 01 is implemented at the site.

Key changes in Protocol Amendment 01 include:

- Details of closure of the study, with provision for participants currently on treatment to continue.
- Clarification that all pharmacokinetic (PK), biomarker, patient-reported outcomes, and health care resource utilization assessments are no longer applicable per Protocol Amendment 01.
- Clarification that study-related efficacy assessment and Pathology Review Committee (PRC) are no longer applicable per Protocol Amendment 01. Sites should continue efficacy assessment as per local standards of care.

Additionally, dose modification criteria and immuno-oncology (I-O) agent management algorithms were updated per the current National Cancer Institute Common Terminology Criteria for Adverse Events (NCI CTCAE) version (v5).

The changes instituted in Protocol Amendment 01 should override any existing protocol requirements in the event of any apparent contraindications.

3.1.2 *Study Hypothesis*

Not applicable per Protocol Amendment 01:

Treatment of high-risk persistent or recurrent NMIBC that is not classified as BCG unresponsive with systemically administered nivolumab in combination with intravesical BCG will result in improvement in EFS when compared with intravesical BCG alone.

3.2 *Background*

3.2.1 Indication Background

Bladder cancer is the ninth most common cancer worldwide, with nearly 430,000 new cases diagnosed in 2012.^{4,5} Bladder cancer ranks as the fifth most commonly diagnosed noncutaneous solid malignancy in the US, estimated to account for 79,000 new cases and almost 17,000 deaths in 2017.⁶ Bladder cancer is more common in men than in women, with a ratio of approximately 3:1.^{6,7} The majority of cases are UC, with mixed or variant histologies (such as squamous cell carcinoma, adenocarcinoma, micropapillary carcinoma, or neuroendocrine carcinoma) comprising a smaller subset.⁸

Approximately 75% to 80% of all bladder cancers present as superficial, non-muscle-invasive disease, while the remaining 20% to 25% are muscle invasive or metastatic at the time of presentation.⁹ NMIBCs are confined to either the mucosal lining or lamina propria of the bladder, not yet having penetrated into the muscular bladder wall (muscularis propria).⁷ Initial treatment for patients with NMIBC includes transurethral resection of the bladder tumor (TURBT). This procedure is therapeutic in that the entire tumor is removed if feasible, and it is also prognostic in that it allows for accurate clinical staging and grading of the tumor. The need for subsequent therapy after TURBT is based on several well-described clinical and pathological risk factors for disease recurrence and progression that can be determined based on endoscopic examination of the bladder and pathologic evaluation of the tumor specimen. These risk factors include tumor grade, stage, size, multiplicity, recurrence rate, and the presence or absence of CIS.⁷ These risk factors have been used to create 3 clinical risk groupings (ie, low, intermediate, and high), which may assist clinicians and patients in determining prognosis and the need for additional therapy after TURBT. High-risk NMIBC includes any high-grade (HG) papillary Ta tumor (TaHG), any grade T1 tumor, and/or the presence of CIS.⁷

Following the initial report of its successful use in bladder cancer patients,¹⁰ intravesical BCG became the SOC as adjuvant treatment for patients with high-risk NMIBC after TURBT. Multiple studies and meta-analyses have demonstrated that a 6-week induction course of intravesical BCG followed by maintenance treatment for 3 years of BCG treatment significantly decreases the risk of bladder tumor recurrence and progression in patients with high-risk NMIBC when compared with no additional treatment or treatment with intravesical chemotherapy.^{7,11,12,13,14,15} Despite the recognized benefit of BCG treatment in this patient population, tumor recurrence and progression within 5 years following BCG induction and maintenance is common, occurring in 40% to 80% (recurrence) and 25% to 45% (progression) of patients.^{16,17,18,19} While some patients will respond to a second induction course, for patients with persistent NMIBC, treatment with BCG beyond 2 induction courses does not have any additional clinical benefit.²⁰

Treatment options for patients with recurrence after initial treatment for high-risk NMIBC with BCG therapy depend on a variety of factors, including timing of recurrence, amount of previous BCG exposure, and stage of disease. Recurrent NMIBC may be suitable for further treatment with BCG, or may be considered BCG unresponsive.

A consensus definition of BCG unresponsive NMIBC has been developed to specifically define the population of patients who will no longer benefit from further BCG treatment (see [Section 6.2.1](#)).^{21,22} Treatment for patients with high-risk NMIBC that is BCG unresponsive remains a challenge. Therapeutic options include radical cystectomy or single/combination agent chemotherapy. The prognosis of this group of patients remains poor, and ongoing studies^{23,24} are addressing this unmet need.

The SOC for patients with high-risk NMIBC who have persistent or recurrent disease after BCG (either induction treatment alone or induction and maintenance treatment with BCG) that is not BCG unresponsive is TURBT followed by retreatment with BCG induction and maintenance.

Patients with recurrence of high-risk NMIBC have a worse prognosis than those with a new diagnosis.²⁵ Outcomes of patients with persistent or recurrent disease that is not BCG unresponsive have not been studied specifically given the recent standardization of this diagnostic categorization. However, available evidence suggests the rate of recurrence in this group of patients may be estimated at approximately 40% at 24 months.²⁶

The natural history of NMIBC is that patients may have repeated episodes of disease recurrence and treatment with resection with or without intravesical treatment, dependent on the risk category. Repeated episodes of disease require tumor resection and intravesical therapy. Patients may become BCG unresponsive and require more aggressive surgery (radical cystectomy), or may progress to un-resectable/metastatic disease and require chemotherapy.

The morbidity and mortality from radical cystectomy is significant, including a 31% perioperative complication rate, a 21% readmission rate, and a 1%-3% mortality rate following the procedure.²⁷ Despite this procedure's potentially curative intent, radical cystectomy is not performed in approximately 50% of indicated patients due to reasons that include advanced age, comorbid conditions, or patient refusal²⁸ and in those patients, treatment options are limited with significant unmet medical need.

For patients who do progress to metastatic disease, the prognosis is poor, and responses to standard platinum based chemotherapy regimens generally are short-lived; the median survival of patients with metastatic disease is approximately 14 - 15 months.²⁹

Patients with persistent/recurrent high-risk NMIBC after treatment with BCG are at higher risk of further recurrence/progression, and are therefore more frequently require radical cystectomy or progress to un-resectable/metastatic disease. New treatment options for persistent/recurrent high-risk NMIBC should reduce or delay subsequent recurrence or progression and therefore the requirement for cystectomy and the occurrence of metastatic disease. The addition of nivolumab with BCG may augment the immunological effect of BCG and provide additional clinical benefit vs BCG alone address this unmet need.

3.2.2 Nivolumab Mechanism of Action

Nivolumab (also referred to as BMS-936558, MDX1106, or ONO-4538) is a human monoclonal antibody (HuMAb; immunoglobulin G4 [IgG4]-S228P) that targets the programmed death-1 (PD-1) cluster of differentiation 279 (CD279) cell surface membrane receptor. PD-1 is a negative regulatory molecule expressed by activated T and B lymphocytes.³⁰ Binding of PD-1 to its ligands, programmed death-ligands 1 (PD-L1) and 2 (PD-L2), results in the down-regulation of lymphocyte activation. Inhibition of the interaction between PD-1 and its ligands promotes immune responses and antigen-specific T-cell responses to both foreign antigens as well as self-antigens. Nivolumab is expressed in Chinese hamster ovary (CHO) cells and is produced using standard mammalian cell cultivation and chromatographic purification technologies. The clinical study product is a sterile solution for parenteral administration.

OPDIVO™ (nivolumab) is approved for the treatment of several types of cancer in multiple regions including the United States (US, Dec-2014), the European Union (EU, Jun-2015), and Japan (Jul-2014).

3.2.3 BCG Mechanism of Action

Although the exact mechanism of action is unknown, the anti-tumor effects of BCG appear to be T-lymphocyte dependent. When administered intravesically to treat bladder cancer, BCG produces a local acute inflammatory reaction and a subacute granulomatous reaction that involves macrophage and lymphocyte infiltration in the mucosal bladder lining (urothelium) and lamina propria of the bladder.

Evidence to date suggests that cells of the immune system, as well as bladder cancer cells themselves, have important roles in the anti-tumor effect of intravesical BCG.³¹ Requirements for effective BCG therapy include an intact immune system, live BCG, and close contact between cancer cells and BCG. BCG's anti-tumor activity appears to be mediated through activation of the immune system and induction of an inflammatory response that includes an influx of immune cells into the bladder wall and release of a wide range of cytokines and chemokines that appear in the urine of BCG-treated patients. CD4+ cells predominate in the urine and bladder mucosa after BCG treatment. However, CD8+ cells are required for effective treatment and natural killer cells, granulocytes, and macrophages are also important constituents of the cellular response to BCG. BCG treatment results in a massive release of cytokines into the urine, including IL-1, IL-2, IL-5, IL-6, IL-8, IL-10, IL-12, IL-18, tumor necrosis factor (TNF), IFN- γ , granulocyte-macrophage colony-stimulating factor (GM-CSF) and TNF-related apoptosis-inducing ligand. Studies also support a role of BCG in the maturation of dendritic cells by signaling through toll-like receptors and secretion of inflammatory cytokines such as IL-12, IFN- γ , and TNF- α .³²

Both bladder cancer cells and benign urothelial cells appear to play a role in the initial recognition and processing of BCG.³¹ Bladder cancer cell attachment to BCG is mediated through fibronectin, leading to BCG internalization and subsequent secretion of immune-activating effectors by cancer cells including IL-6, IL-8, GM-CSF, and TNF. Bladder cancer cells also may function as antigen-presenting cells for BCG, and BCG may have direct cytotoxic effects on bladder cancer cells.

For additional information on the mechanism of action of live BCG (intravesical), see the current prescribing information (Summary of Product Characteristics [SmPC], United States [US] Prescribing Information [USPI], or country-specific label).

3.3 Benefit/Risk Assessment

There is significant unmet need in patients who have persistence or recurrence of high-risk NMIBC that is not BCG unresponsive. New therapies are required to reduce the rate of recurrence, cystectomy, and progression to metastatic disease.

There is evidence for the efficacy of nivolumab in UC and proof of concept for PD-1 inhibition in NMIBC:

- In metastatic UC, nivolumab as monotherapy has received accelerated approval in the US for the treatment of patients with locally advanced or metastatic UC who have had disease progression during or following platinum-containing chemotherapy or who have had disease progression within 12 months of neoadjuvant or adjuvant treatment with platinum-containing chemotherapy. It has received approval in the EU for the treatment of locally advanced unresectable or metastatic UC in adults after failure of prior platinum-containing therapy. See the current prescribing information for nivolumab (Opdivo®) for more information.
- In NMIBC, preliminary evidence of clinical activity of PD-1 inhibition comes from study Keynote-057, a single-arm study of pembrolizumab in BCG-unresponsive NMIBC.²⁶ In the interim analysis of this study, the response rate of CIS participants treated with pembrolizumab monotherapy was 39% at Month 3, with 80.2% of participants having a CR duration of \geq 6 month.³³ The safety profile was consistent with the profile of pembrolizumab across tumor types. These data are clinically significant in a group of participants for whom there are no effective intravesical or systemic treatment options, and cystectomy is the SOC.

In addition, the safety profile of both nivolumab and BCG are both well characterized.

Extensive details on the safety profile of nivolumab are available in the Investigator's Brochure (IB) and will not be repeated herein.

Overall, the safety profile of nivolumab monotherapy is manageable and generally consistent across completed and ongoing clinical trials with no maximum tolerated dose (MTD) reached at any dose tested up to 10 mg/kg. Most adverse events (AEs) were low grade (Grade 1 to 2) with relatively few related high-grade (Grade 3 to 4) AEs. There was no pattern in the incidence, severity, or causality of AEs with respect to nivolumab dose level.

A pattern of immune-mediated AEs (IMAEs) has been defined, for which management algorithms have been developed; these are provided in [Appendix 5](#). Most high-grade events were manageable with the use of corticosteroids or hormone replacement therapy (endocrinopathies) as instructed in these algorithms.

Additional details on the safety profile of nivolumab, including results from other clinical studies, are also available in the nivolumab IB.

The incidence and pattern of BCG-related adverse effects are well characterized and are presented in the current prescribing information.

The safety and tolerability of nivolumab in combination with intravesical BCG is currently unknown. BMS study CA2099UT²³ is examining the combination of nivolumab with BCG in participants with BCG unresponsive high-risk NMIBC. At the time of protocol writing, the first 8 participants treated with nivolumab plus BCG in study CA2099UT have passed the dose-limiting toxicity evaluation period and been reviewed by the Data Monitoring Committee (DMC) (data on file, May 2019). The study is continuing unchanged.

To ensure an ongoing favorable benefit/risk assessment for participants enrolled into the present study, the following safety measures will be employed throughout the conduct of the study:

- Institution of an external DMC to provide independent oversight of safety, study conduct, and benefit/risk assessment of nivolumab in combination with BCG
- Rigorous safety monitoring by BMS to ensure participants' safety, including regular and systematic review of safety data, close follow-up of reported AEs, and intensive site and study investigator training/education on the implementation of the nivolumab and BCG toxicity management strategies

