BCG can be delayed, modified, or discontinued for BCG-related toxicity. Administration of BCG should not be delayed if nivolumab/nivolumab-placebo treatment is delayed.

The **follow-up phase** will begin when the decision to discontinue a participant from the last study treatment is made or when 3 years of study treatment has been completed. There will be a standard safety follow-up for a minimum of 100 days after last dose of last study treatment.

Not applicable per Protocol Amendment 01:

Survival follow-up begins after safety follow-up, with visits every 3 months until the end of the study. Efficacy assessments will occur until disease recurrence (other than low-grade Ta) or progression per PRC (based on a positive urinary cytology, bladder biopsy, or imaging) or treatment discontinuation, whichever is later.

Data Monitoring Committee: Yes; however, no longer applicable per Protocol Amendment 01

References:

- ¹ US Department of Health and Human Services, Food and Drug Administration, Center for Drug Evaluation and Research, Center for Biologics Evaluation and Research. BCG-unresponsive non-muscle invasive bladder cancer: Developing drugs and biologics for treatment guidance for industry. February 2018 (Accessed June 18, 2019).
- ² Steinberg RL, Thomas LJ1, Mott SL, O'Donnell MA. *Bacillus Calmette-Guérin (BCG) treatment failures with non-muscle invasive bladder cancer: A data-driven definition for BCG unresponsive disease.* Bladder Cancer 2016;2(2):215-24.

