5 STUDY DESIGN

5.1 Overall Design

[figure not shown]
This is a Phase 3, randomized, double-blind, international, multicenter study of nivolumab in combination with BCG vs nivolumab-placebo with BCG in adult participants with high-risk NMIBC that is persistent or recurrent after treatment with BCG and does not qualify as BCG unresponsive.²¹

The study design schematic is presented in [Figure 5.1-1](#).

Figure 5.1-1: CA2097G8 Study Design Schematic

Stratification:

1. Histology: CIS (+/- papillary) vs T1
2. Time to recurrence from last BCG dose: Early vs Late
3. Intended BCG strain: TICE vs Other

The study will proceed through 3 phases: screening, treatment, and follow-up.

As of 02-Jun-2021, enrollment into this study was closed. Protocol Amendment 01 removes the decision points and the efficacy follow-up along with other study procedures. As a result, initial benefit/risk assessment by the Data Monitoring Committee (DMC) and PRC will be removed.

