5.1.4 Data Monitoring Committee and Other External Committees

Not applicable per Protocol Amendment 01:

An independent, external DMC will be established to provide oversight of safety and efficacy considerations in this protocol and to provide advice to the Sponsor regarding actions the committee deems necessary for the continued protection of participants enrolled in the study. The DMC will be charged with assessing such actions in light of an acceptable benefit/risk profile for nivolumab and nivolumab-placebo plus BCG. The DMC will act in an advisory capacity to BMS and will monitor participant safety and evaluate the available efficacy data for the study. Data and summaries will be made available to the DMC. The BMS Oncology Clinical Development Department has primary responsibility for design and conduct of the study.

Additional details concerning DMC oversight are provided in the DMC charter.

Pathology Review Committee

Not applicable per Protocol Amendment 01:

An independent PRC will review cystoscopy reports, imaging reports, participant biopsy slides, and urinary cytology obtained prior to randomization to confirm the diagnosis of high-risk

NMIBC. Similarly, on-study cystoscopy and imaging reports, biopsies, and urine cytology will be submitted to the PRC to exclude or confirm recurrence or progression.

Additional details concerning PRC responsibilities are provided in the PRC charter and in [Section 9.1.8](#).

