7.3 Blinding

As of Protocol Amendment 01, it has been determined that blinding is not required. In both scenarios where the investigators may break the blind in the best interest of the participant or in case of accidental unblinding, IRT instructions should be followed along with a notification to the Medical Monitor.

This is a randomized, double-blind study. Access to treatment codes will be restricted from all participants and site and BMS personnel prior to final database lock, with exceptions as specified below. Each investigative site must assign an unblinded pharmacist/designee, and an unblinded site monitor will be assigned to provide oversight of drug supply and other unblinded study documentation.

To further minimize bias, the investigative clinical site staff is masked to results from PD-L1 analysis.

Blinding of treatment assignment is critical to the integrity of this clinical study. However, in the event of a medical emergency or pregnancy in an individual participant in which knowledge of the investigational product is critical to the participant's management, the blind for that participant may be broken by the investigator. The participant's safety takes priority over any other considerations in determining if a treatment assignment should be unblinded.

Before breaking the blind of an individual participant's treatment, the investigator should determine that the unblinded information is necessary, ie, that it will alter the participant's immediate management. In many cases, particularly when the emergency is clearly not related to the investigational product, the problem may be properly managed by assuming that the participant is receiving active product. It is highly desirable that the decision to unblind treatment assignment

be discussed with the Medical Monitor, but the investigator always has ultimate authority for the decision to unblind. The actual TASK of unblinding can be delegated by the investigator to a designee assigned the task on the Delegation of Authority. The Principal Investigator or appointed designee should only call in for emergency unblinding AFTER the decision to unblind the participant has been documented.

For this study, the method of unblinding for emergency purposes is through the IRT. For information on how to unblind in an emergency, consult the IRT manual.

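### Does withdrawing the Data Monitoring Committee while Section 3.3 still relies on it leave safety by arm unwatched until database lock?

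*Combined protocol and SAP*

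**What the plan says.** Section 3.3 (Benefit/Risk Assessment) states that "The safety and tolerability of nivolumab in combination with intravesical BCG is currently unknown". It then says that "the following safety measures will be employed throughout the conduct of the study" and gives two. The first is "Institution of an external DMC to provide independent oversight of safety, study conduct, and benefit/risk assessment of nivolumab in combination with BCG". The second is safety monitoring by the sponsor, with regular review of safety data and close follow-up of adverse events. Nothing in 3.3 is marked as no longer applicable.

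Elsewhere Amendment 01 withdraws the committee:

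- Synopsis, Data Monitoring Committee: "Yes; however, no longer applicable per Protocol Amendment 01".
- Section 5.1: "initial benefit/risk assessment by the Data Monitoring Committee (DMC) and PRC will be removed".
- Section 5.1.4: the sentence "An independent, external DMC will be established to provide oversight of safety and efficacy considerations in this protocol" now stands under a not-applicable label.

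Section 7.3 (Blinding) opens with the amended position, "As of Protocol Amendment 01, it has been determined that blinding is not required". The older text follows unmarked, including "Access to treatment codes will be restricted from all participants and site and BMS personnel prior to final database lock". The only exceptions for sponsor staff concern bioanalytical work on pharmacokinetic and immunogenicity samples, which the amendment has discontinued.

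The Synopsis and Section 3.1.1 say that Amendment 01 prevails over existing requirements where they clash. Participants already on treatment may continue, for up to three years of study treatment.

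**The concern.** Section 3.3 justifies exposure to a combination of unknown safety by two safeguards. The first no longer exists. The second looks weakened if sponsor staff cannot see treatment codes before database lock. On that reading no one is assigned to compare toxicity between arms during the remaining treatment period. An excess of immune-mediated or BCG-related events on nivolumab would then be seen by arm only when it was too late to alter anyone's treatment. Participants must also be re-consented under Amendment 01, and the benefit/risk text in the protocol still cites a committee that has been stood down.

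**Working it through.** The plan gives no figure to reproduce. The check has four parts: a comparison of texts, then the length of the window, the number of participants, and what a by-arm table could show.

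**1. Do the texts bar by-arm review?**

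| Place | Position | Origin |
|---|---|---|
| Synopsis; 5.1; 5.1.4 | Committee withdrawn | Amendment 01 |
| 3.3, first safeguard | Committee throughout the study | Older text, not updated |
| 3.3, second safeguard | Regular sponsor safety review | Still in force |
| 7.3, opening | Blinding not required | Amendment 01 |
| 7.3, following text | Codes restricted until database lock | Older text, not marked |
| Synopsis; 3.1.1 | Amendment 01 prevails in a conflict | Amendment 01 |

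The precedence clause is worded for apparent contraindications, which in context must mean contradictions. It settles 3.3 against the committee bullet. In 7.3 it favours the opening sentence over the older restriction. Sponsor access to codes is therefore unreconciled, not prohibited. What the texts do not supply is a named reviewer of by-arm tables during treatment.

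**2. How long do the arms differ?**

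- BCG (Table 7.1.2-1): the last dose is Week 159 Day 1, so 158 × 7 + 1 = day 1107. Adding 100 days of follow-up gives day 1207, and 1207 / 365.25 = 3.30 years.
- Nivolumab or placebo (Table 2-2): Cycle 26 Day 1 is 25 × 28 + 1 = day 701. Adding 100 days gives day 801, and 801 / 365.25 = 2.19 years.

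BCG is given in both arms, so the randomized difference in dosing and its 100-day follow-up end at about 2.2 years. The remaining 1207 − 801 = 406 days are BCG alone in everyone. Both figures run from a participant's first dose and assume no delay, recurrence or early stop.

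**3. How many participants?**

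The Synopsis and 3.1.1 put enrollment below 5% of target.

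- If the target is 700 randomized: 0.05 × 700 = 35.
- If it is 875 enrolled with 20% screen failure: 0.05 × 875 × 0.80 = 35.

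Either reading gives fewer than about 35 randomized, plus any participants then in screening who went on to randomization.

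**4. What could a by-arm table show?**

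The arm sizes are an assumption: 17 or 18 each. The event rates are illustrative and do not come from the protocol. Power of a two-sided Fisher exact test at 0.05, by summing over all possible tables:

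| True rates | Power across 17/17, 17/18, 18/17 and 18/18 |
|---|---|
| 5% vs 20% | 12% to 22% |
| 10% vs 30% | 19% to 28% |

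A single look would miss a fourfold or threefold excess most of the time.

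**The case for a change.** The strongest reply is that a precedence clause can delete a committee but cannot appoint its successor. Section 5.1.4 had given the committee the task of monitoring safety on data supplied to it. Section 10.3.2 now promises safety tables by treatment group but names neither a reviewer nor an interval. The new sentences in 7.3 deal with an investigator breaking the blind and with accidental unblinding, not with sponsor access to aggregate data, so two readers could take 7.3 in opposite senses. In so small a study the value of review lies in reading individual cases with treatment known, not in a test, and the cost would be slight.

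Much of this stands. The bullet in 3.3 is out of date, 7.3 disagrees with itself, and no by-arm reviewer is named.

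The inference to unprotected participants does not stand. Section 9 requires immediate discussion of safety concerns with the sponsor. Section 9.2.1 and Appendix 3 require serious events to be reported within 24 hours, and Section 9.2.4 covers expedited reporting to authorities and investigators. Table 7.4-1 drives dosing decisions from the individual's event and grade, and Section 7.4.3.1 applies the delay rules whichever agent is blamed, so action on toxicity does not wait for a comparison of arms. Section 7.3 lets the investigator unblind a participant in that person's interest. Case-level review with treatment known is therefore already open.

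The consent argument cannot be tested: the consent form is not among the documents, and the Synopsis, 5.1 and 5.1.4 all state the withdrawal openly.

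**Conclusion.** The concern does not call for a change to the plan. Two remnants of older text survive the amendment: the committee bullet in 3.3 and the code restriction in 7.3. Both give way to Amendment 01 under its own precedence clause, so the first is a clerical slip and the second an ambiguity that a reader would resolve sensibly. The missing name of a by-arm reviewer is a detail left to the sponsor's continuing safety review. Scheduled unblinded tables would be a preference. At the assumed 17 or 18 per arm they would have roughly 12% to 28% power for the differences shown, and they would not restore the independence that went with the committee.

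No estimate, test or conclusion turns on any of this. Section 10 limits the analysis to descriptive safety and listings of investigator-assessed efficacy, and Section 3.1.1 attributes closure to slow enrollment, with no change in what is understood about the combination's safety.

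The judgement rests on the precedence clause covering conflicts between texts, on about 35 randomized participants, and on the sponsor carrying out the safety review that 3.3 still commits it to. If many more participants were on treatment, or the precedence clause were absent, the unnamed reviewer would matter more.
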